5.6.4 Adverse events leading to discontinuation of study treatment

These are AEs with ‘Action taken with study drug’ recorded as ‘permanently discontinued’ on the **Adverse Event** eCRF.

5.6.5 Other adverse events

Not applicable.

5.6.6 Physical examination, vital signs and body weight

Vital signs include PR measured by BpTRU[®] (simultaneously with BP; the mean is provided in the same way, i.e., based on the last 5 of 6 measurements) and body weight (DBP and SBP are evaluated as efficacy endpoints). For PR, the value is retrieved from the SDTM VS domain by selecting VSTESTCD = “HR” and VSSCAT = ‘Average’.

All assessments (including the unscheduled ones) are considered and re-assigned to the most appropriate visit according to the time windows described in Section 12.

5.6.7 Electrocardiogram

A standard 12-lead ECG is performed as defined in the Schedule of Assessments. Historical ECG is accepted for Visit 1, if not older than 6 months. Digital 12-lead ECG devices will be provided to each site by the central ECG laboratory for the duration of the study. All assessments (including the unscheduled ones) are considered and re-assigned to the most appropriate visit according to the rules described in Section 11.1.

The following variables will be evaluated: heart rate (HR; bpm), PR (ms), QRS (ms), QT (ms), QTc (ms). In addition, the percentage of subjects with any ECG findings will be evaluated.

QTc (ms) will be calculated according to Fridericia’s formula $QTcF = QT/(RR)^{1/3}$.

ECG data will be electronically transferred from the ECG laboratory database to Actelion and will not be (re-)calculated. Note that ECG HR will be evaluated only in the context of the ECG. For vital signs, PR will be used based on BpTRU[®].

5.6.7.1 Treatment-emergent ECG abnormalities

Double-blind treatment-emergent ECG abnormalities are defined as follows:

- QTcF (Fridericia's formula) maximum value > 450 ms (H), > 480 ms (HH), or > 500 ms (HHH);
- Maximum increase from baseline in QTcF (Fridericia's formula) > 30 ms (HH), > 60 ms (HHH).

In addition, each of the six combinations of maximum QTcF and increase in QTcF will be considered.

Note that, in order to allow appropriate interpretation of overall incidence of abnormalities > 450 ms, the marked abnormalities are presented cumulatively, e.g., a QTc value of 501 ms is reported in > 450 ms (H), > 480 ms (HH) and > 500 ms (HHH) categories; the same holds for abnormalities related to changes from baseline (i.e., they are presented cumulatively).

Treatment-emergent ECG abnormalities are defined as those abnormalities with onset on or after the double-blind treatment start date [see definition in Section 11.2] up to the double-blind treatment end date [see definition in Section 11.4] plus 30 days (included): i.e., the highest QTc absolute value and the highest QTc change value at any post-baseline time point of assessment up to 30 days after study treatment discontinuation are considered in the evaluation of the categories, as defined above.

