7.3.3 ECG assessments

A standard 12-lead ECG is performed as defined in Table 1, Schedule of Assessments. Historical ECG is accepted for Visit 1, if not older than 6 months. Digital 12-lead ECG devices will be provided to each site by the central ECG laboratory for the duration of the study.

The following variables will be evaluated: HR (bpm), PR (ms), QRS (ms), QT (ms), QTc (ms), and any ECG findings. QTc (ms) will be calculated according to Bazett's and Fridericia's formula (QTcB = QT/(RR) ½ and QTcF = QT/(RR) ⅓, respectively).

ECG findings made after study start which meet the definition of an AE [Section 10.1.1] must be recorded by the investigator on the AE page of the eCRF.

The data records will be electronically transmitted to the central ECG laboratory for central reading. The reports from the central ECG laboratory will be sent to the site within a few days. Details on ECG procedure (recording, transfer of data and reporting to the site) will be provided in the ECG manual.

ECG data will be electronically transferred from the ECG laboratory database to Actelion.

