11.3.5.1 Adverse events

A treatment-emergent AE is any AE temporally associated with the use of a study drug. Treatment-emergent is defined as in Section 10.1.1. The number and percentage of subjects experiencing treatment-emergent AEs and SAEs at least once will be tabulated by treatment group and by:

- MedDRA System Organ Class (SOC) and individual Preferred Term (PT) within each SOC, in descending order of incidence.
- Frequency of subjects with events coded with the same PT, in descending order of incidence.

Furthermore, treatment-emergent AEs and SAEs will be tabulated as described above by severity and relationship to study drug.

Essential hypertension Protocol AC-080A201 Version 3 30 May 2016, page 89/112

Confidential

AEs leading to premature discontinuation of study drug and death will also be summarized as described above.

Listings will be provided for all reported AEs, including SAEs. In addition, separate listings will be provided for SAEs, for AEs leading to premature discontinuation of study drug, and for AEs leading to death.

The number and percentage of subjects with treatment-emergent ECG abnormalities will be tabulated by treatment group.

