11.3.5.2 Laboratory parameters

Descriptive summary statistics by visit and treatment group will be provided for observed values and absolute changes from baseline, in both hematology and blood chemistry and urine (only UACR) laboratory tests. In order to minimize missing data and to allow for unscheduled visits, all recorded assessments will be assigned to the most appropriate visit timepoint according to the best fitting time-window for that assessment.

Actelion internal guidelines will be used for the definitions of marked abnormalities and for the standardization of numeric values obtained from different laboratories and/or using different normal ranges. Standard numeric laboratory variables are transformed to standard units. All laboratory data transferred are taken into account regardless of whether they correspond to scheduled (per protocol) or unscheduled assessments.

Marked laboratory abnormalities will be summarized for each laboratory parameter by treatment group providing their incidence and frequency. Absolute values and changes from baseline of laboratory parameter values during the course of the study will be summarized using the usual location and scale summary statistics by treatment group.

Laboratory parameters include:

- Hematology: hemoglobin, hematocrit, erythrocyte count, leukocyte count with differential counts, platelet count.
- Blood chemistry: AST, ALT, alkaline phosphatase, total and direct bilirubin, LDH, creatinine, creatinine clearance, uric acid, glucose, sodium, potassium, protein, albumin, free T3, free T4, TSH.
- Urine: UACR.

The number and percentage of subjects with treatment-emergent laboratory abnormalities will be tabulated by treatment group.

Essential hypertension Protocol AC-080A201 Version 3 30 May 2016, page 90/112

Confidential

11.3.5.3 12-lead ECG

Descriptive statistics by visit and treatment group will be provided for observed values and absolute changes from baseline, in numeric 12-lead ECG values (PR, QRS, QT, QTcB and QTcF). In order to minimize missing data and to allow for unscheduled visits, all recorded assessments will be assigned to the most appropriate visit time point according to the best fitting time-window for that assessment.

In addition, treatment-emergent morphological ECG abnormalities will be summarized.

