13.10 Electrocardiogram (ECG)

Output name	Display *	Title (Description)	Analysis set(s)	Key	Mock layout
ECG_CHG	T	ECG parameters: changes from baseline to end of double-blind treatment	SAF		LAYBASE001
ECGQTCP T	T	Number of subjects with double-blind treatment-emergent ECG abnormalities (based on Fridericia's formula)	SAF		LAYECG001
ECGMA	L	Listing of 12-lead ECG variables in subjects with at least one double-blind treatment-emergent ECG abnormalities	SAF		LSTCSR0931
ECG	L	Listing of 12-lead ECG variables and abnormalities	SCR		LSTCSR093

* T = Summary Table; L = Listing.
ECG = electrocardiogram; SAF = Safety Set; SCR = Screened Set.

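### The SAP defines treatment-emergent ECG abnormalities by QTcF alone and plans no by-arm table for the morphological ECG summary that the protocol promises

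*SAP*

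**What the plan says.** **Protocol.** Treatment-emergent ECG abnormalities are a safety endpoint in 6.2 and 11.2.4, listed separately from treatment-emergent adverse events. Section 7.3.3 names what is evaluated on each tracing: "The following variables will be evaluated: HR (bpm), PR (ms), QRS (ms), QT (ms), QTc (ms), and any ECG findings". The tracings go to a central laboratory for reading and the data are transferred to the sponsor. Section 11.3.5.1 states: "The number and percentage of subjects with treatment-emergent ECG abnormalities will be tabulated by treatment group". Section 11.3.5.3 covers the numeric ECG values by visit and treatment group and then adds: "In addition, treatment-emergent morphological ECG abnormalities will be summarized".

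**SAP.** Section 5.6.7 lists the ECG variables and says: "In addition, the percentage of subjects with any ECG findings will be evaluated". The next section, 5.6.7.1, opens with "Double-blind treatment-emergent ECG abnormalities are defined as follows" and gives two criteria. The first is "QTcF (Fridericia's formula) maximum value > 450 ms (H), > 480 ms (HH), or > 500 ms (HHH"). The second is a maximum QTcF increase of more than 30 or more than 60 ms. Section 10.9.3 summarizes abnormalities under that definition by treatment group. Section 13.10 lists a table titled "Number of subjects with double-blind treatment-emergent ECG abnormalities", qualified as based on Fridericia's formula, and a table titled "ECG parameters: changes from baseline to end of double-blind treatment". It also lists two listings. Section 4.1.3, which records changes to the planned safety analysis, mentions only the added dose-response analyses of hemoglobin and body weight.

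**The concern.** The protocol promises a summary that the SAP does not produce. A subject whose baseline tracing is normal and whose on-treatment tracing shows, say, a new conduction or repolarization abnormality with a QTcF below the thresholds is not an event under SAP 5.6.7.1. No other ECG table counts that subject.

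Safety and tolerability of the four doses is a secondary objective, and the study is meant to select Phase 3 doses. A summary by dose group is the natural place to look for a dose-related pattern in such findings. The adverse-event tables cover part of this ground, but they depend on the investigator judging a finding clinically significant and reporting it. The protocol treats the ECG abnormality summary as a separate item.

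**Working it through.** No sample-size, power or event figure bears on this point, so the check is a comparison of the texts.

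| Item | Protocol | SAP definition | SAP analysis (10.9.3) | SAP output (13.10) |
|---|---|---|---|---|
| QTcF abnormalities | Within ECG abnormalities (11.3.5.1) | 5.6.7.1 | By arm, n (%) with 95% limits | One table |
| Morphological abnormalities, treatment-emergent | Summary (11.3.5.3) | None | None | Listing only |
| Any ECG finding, percentage | Evaluated as a variable (7.3.3) | 5.6.7, with no treatment-emergent rule | None | None |
| Changes in ECG parameters | Weeks 4 and 8 (6.2, 11.2.4) | 5.6, Weeks 4 and 8 | None | One table (ECG_CHG), titled to end of double-blind treatment |

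**Step 1: content of the definition.** SAP 5.6.7.1 has 3 absolute QTcF levels and 2 QTcF increases. It states that six combinations are considered, and 3 × 2 = 6 agrees. The number of morphological categories is 0.

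**Step 2: outputs.** SAP 13.10 has 4 ECG outputs, 2 tables and 2 listings. One table is the Fridericia-based count and the other is ECG_CHG. Tables that count morphological findings by arm: 0 of 2. The ECGMA listing is restricted to subjects with a treatment-emergent abnormality as defined in 5.6.7.1, so it selects on QTcF. Other abnormalities reach only the general ECG listing on the Screened Set.

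**Step 3: the SAP's own promise.** The percentage with any ECG finding in 5.6.7 has no baseline comparison, treatment-emergent window or by-arm statement. It is not taken up in 10.9.3 or 13.10. The SAP intended a count and did not specify it.

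**Step 4: declaration.** SAP 4.1.3 declares no ECG change, so the missing summary is not presented as a decision.

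**Step 5: what is still counted by arm.** Under protocol 7.3.3 and 10.1.1, an ECG finding that is clinically significant and new or worsened is recorded as an adverse event. SAP 10.9.1 and 13.9.1 count treatment-emergent adverse events by treatment group, system organ class and preferred term. SAP 13.10 tabulates ECG parameter changes on the Safety Set. What remains is centrally read morphological findings that the investigator does not report as adverse events.

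**Step 6: visits.** SAP 5.6 keeps changes to Weeks 4 and 8, as the protocol does, but the ECG_CHG title names only the end of double-blind treatment. The hematology and chemistry change tables in 13.11 refer to post-baseline visits instead. The layout assigned to ECG_CHG is also used for by-visit tables such as DBP_CHG, so the layout does not settle which is meant.

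**The case against.** The strongest reply is that the safety data are not lost. A clinically significant rhythm or conduction disturbance is an adverse event and is counted by arm. A dose-related shift in PR or QRS, the numeric sign of a conduction effect, would appear in ECG_CHG. This stands, and it confines the gap to findings that are neither reported as adverse events nor visible in the intervals.

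A second reply is that the protocol never defines treatment-emergent ECG abnormalities and leaves full analysis details to the SAP (protocol section 11), so the SAP may choose a QTcF definition. That also stands for the endpoint's name. It does not dispose of the morphological summary, which 11.3.5.3 promises separately and which the SAP neither provides nor withdraws.

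A reader might infer more than the documents support:

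- That new arrhythmia, conduction or ST-T findings are never counted by arm, or that any non-QTcF signal can be seen only in listings. The adverse-event tables and ECG_CHG contradict both.
- That the two documents hold conflicting definitions of an ECG event. The protocol has no formal definition to conflict with.
- That the SAP dropped the Week 4 ECG endpoint. SAP 5.6 retains it; only the output title is out of line.

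**Conclusion.** The point holds as a completeness gap. A morphological ECG summary promised in the protocol, and an any-finding percentage promised in the SAP itself, have no treatment-emergent rule, analysis text or table, and the omission is undeclared. The consequence is limited to centrally read morphological findings not reported as adverse events, which would appear only in a listing.

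Its size cannot be expressed in subjects. It is tempting to apply an assumed incidence to the 490 randomized subjects (SAP 4.2). However, the documents give no incidence for such findings and no share that would also be adverse events, so any count would be guesswork.

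The conclusion assumes that the summary in protocol 11.3.5.3 was meant by treatment group. That section describes the numeric values that way, and 11.3.5.1 says so for ECG abnormalities generally. Severity is minor: this is a descriptive safety analysis in Phase 2, and other by-arm tables cover part of the same ground.

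**What to change.** 1. In SAP 5.6.7.1, add a category: a centrally read morphological abnormality absent on the baseline ECG and first present after the start of double-blind treatment, within the existing window to 30 days after its end. The window there points to SAP 11.2 and 11.4, which are run-in start and randomization; the double-blind start and end are in 11.5 and 11.6. Correct this in the same edit.
2. In SAP 10.9.3 and 13.10, add one Safety Set table of n (%) by finding category and treatment group. State whether it also serves as the any-finding percentage of 5.6.7.
3. Reword the ECG_CHG title in 13.10 to name Weeks 4 and 8, in line with SAP 5.6 and the protocol.

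If the sponsor prefers not to produce the table, SAP 4.1.3 should declare and justify the omission.

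The cost is one table and a few lines of SAP text. No new data collection is needed, provided the central laboratory's transfer carries the findings as well as the intervals. Protocol 7.3.3 and the planned listing of ECG abnormalities indicate that it does.

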5.6.8.1 Treatment-emergent marked laboratory abnormalities

The marked laboratory abnormalities are given in [Table 2](#), copied from appendix 1 of the protocol.

Table 2 **Thresholds for marked laboratory abnormalities**

Parameter	LL	LLL	HH	HHH	HHHH
Hematology					
Hemoglobin	< 100 g/L (< 10 g/dL; < 6.2 mmol/L)	< 80 (< 8 g/dL; < 4.9 mmol/L;)	Increase in > 20 g/L above ULN or above baseline if baseline is above ULN	Increase in > 40 g/L above ULN or above baseline if baseline is above ULN	
Hematocrit	< 28% for females < 32% for males	< 20%	> 60% in men > 55% in women	> 65%	
Leukocytes	< $3.0 \times 10^9/L$ (< 3000/mm ³)	< $2.0 \times 10^9/L$ (< 2000/mm ³)	> $20.0 \times 10^9/L$ (> 20,000/mm ³)	> $100.0 \times 10^9/L$ (> 100,000/mm ³)	
Platelet count	< $75 \times 10^9/L$ (< 75,000/mm ³)	< $50 \times 10^9/L$ (< 50,000/mm ³)	> $600 \times 10^9/L$	> $999 \times 10^9/L$	
Neutrophils	< $1.5 \times 10^9/L$ (< 1500/mm ³)	< $1.0 \times 10^9/L$ (< 1000/mm ³)	NA	NA	
Eosinophils	NA	NA	> 5.0×10^9 or > 5% (> 5000 cells/mm ³)	NA	
Lymphocytes	< $0.8 \times 10^9/L$ (< 800/mm ³)	< $0.5 \times 10^9/L$ (< 500/mm ³)	> $4.0 \times 10^9/L$ (> 4000/mm ³)	> $20 \times 10^9/L$ (> 20,000/mm ³)	

Parameter	LL	LLL	HH	HHH	HHHH
Blood Chemistry					
AST (U/L)	NA	NA	> 3 × ULN	> 5 × ULN	> 8 × ULN
ALT (U/L)	NA	NA	> 3 × ULN	> 5 × ULN	> 8 × ULN
AP	NA	NA	> 2.5 × ULN	> 5 × ULN	
Bilirubin Total (µmol/L)	NA	NA	> 2 × ULN	> 5 × ULN	
Creatinine	NA	NA	> 1.5 × ULN or > 1.5 × baseline	> 3 × ULN or > 3 × baseline	
Creatinine clearance	< 60 mL/min	< 30 mL/min	NA	NA	
Glucose	< 3.0 mmol /L (< 55 mg/dL)	< 2.2 mmol /L (< 40 mg/ dL)	> 8.9 mmol /L (> 160 mg/dL)	> 13.9 mmol /L (> 250 mg/ dL)	
Sodium		< 130 mmol/L (< 130 mEq/L)	> 150 mmol/L (> 150 mEq/L)	> 155 mmol/L (> 155 mEq/L)	
Potassium	< 3.2(mmol/L)	< 3.0(mmol/L)	> 5.5(mmol/L)	> 6.0(mmol/L)	
Uric acid	NA	NA	> 590 (umol/L) (> 10 mg/dL)	> 720 (umol/L) (> 12 mg/dL)	
Albumin	< 30 g/L (< 3.0 g/dL)	< 20(g/L (< 2.0 g/dL)	-	-	

ALT = alanine aminotransferase; AP = alkaline phosphatase; AST = aspartate aminotransferase; NA = not applicable; ULN = upper limit of normal.

Treatment-emergent marked laboratory abnormalities are those marked abnormalities with onset date after the double-blind treatment start date [see definition in Section 11.2] and before or on double-blind treatment end date [see definition in Section 11.4] plus 30 days (included), that were not present at baseline.

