10.9.3 Electrocardiography (ECG)

Double-blind treatment-emergent ECG abnormalities [see definition in Section 5.6.7.1] will be summarized, by treatment group, displaying counts and percentages of subjects (and 95% confidence limits according to the Clopper-Pearson method) with at least one treatment-emergent ECG abnormality. Values from unscheduled visits are included. Subjects may be included in more than one category as the marked abnormality are presented cumulatively.

ECG variables are displayed in a subject listing on the SCR set; a separate listing is provided of all ECG variables, restricted to subjects with at least one abnormality [see Section 5.6.7 for details].

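### SAP 5.6.7.1 requires onset on treatment but fills the three absolute QTcF categories from the highest post-baseline value with no baseline condition, so QTcF prolongation already present at baseline is counted as treatment-emergent in those rows.

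*SAP*

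**What the plan says.** SAP 5.6.7.1 sets two kinds of QTcF abnormality. One is a maximum value above 450, 480 or 500 ms (H, HH, HHH). The other is a maximum increase from baseline above 30 or 60 ms. In addition, "each of the six combinations of maximum QTcF and increase in QTcF will be considered". The categories are shown cumulatively, and the SAP's own example is a value of 501 ms reported in all three absolute rows.

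The closing paragraph opens with a timing condition: "Treatment-emergent ECG abnormalities are defined as those abnormalities with onset on or after the double-blind treatment start date", running to 30 days after the end of double-blind treatment. The same sentence then states how this is to be done: "the highest QTc absolute value and the highest QTc change value at any post-baseline time point of assessment", within those 30 days, is used to evaluate the categories.

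For laboratory values, SAP 5.6.8.1 uses the same 30-day window but keeps only abnormalities "that were not present at baseline".

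SAP 10.9.3 carries the ECG definition into the analysis: "Double-blind treatment-emergent ECG abnormalities [see definition in Section 5.6.7.1] will be summarized, by treatment group", with counts, percentages and Clopper-Pearson limits. It adds no baseline condition. SAP 13.10 lists a table of ECG changes from baseline, the table of abnormality counts and two listings, but no shift table.

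**The concern.** The paragraph gives two rules that disagree. An onset condition would leave out a subject whose QTcF was already prolonged before randomization. A rule based only on the highest post-baseline value would count that subject. The second is the operational statement, so it is the one a programmer is likely to code.

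Nothing elsewhere removes such subjects. The exclusion criteria in Protocol 4.4 contain no QTc limit. The maximum is taken over scheduled ECGs at Weeks 4, 8 and 10 plus any unscheduled ones, so a subject near or above 450 ms at baseline has several chances to exceed it again.

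The result is a table whose label says treatment-emergent but whose absolute rows mix old and new prolongation. In the same report the laboratory tables would use that term in the narrower sense. Protocol 10.1.1, to which Protocol 11.2.4 refers for the meaning of the term, also treats an abnormal ECG as an adverse event only if it is new or has worsened.

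**Working it through.** The plan states no figure on this point, so there is none to reproduce. The check applies the rules to example subjects and then illustrates the possible size.

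**1. Rules applied to example subjects (QTcF in ms)**

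The SAP rule flags a row when the post-baseline maximum exceeds the limit. The laboratory-type rule adds that baseline must not exceed the same limit. The category-worsening rule flags all rows reached, but only if the worst post-baseline category is above the baseline category.

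| Baseline | Post-baseline | Maximum change | SAP rule | Laboratory-type rule | Category-worsening rule |
|---|---|---|---|---|---|
| 455 | 452, 448, 453 | -2 | >450 | none | none |
| 455 | 482, 460, 450 | +27 | >450, >480 | >480 only | >450, >480 |
| 440 | 452, 449, 445 | +12 | >450 | >450 | >450 |
| 455 | maximum 501 | +46 | all three | >480, >500 only | all three |

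In the first line the QTcF never rose above its baseline, yet the SAP rule counts it. That subject cannot enter the >30 or >60 ms rows. Nor can it enter any of the 3 x 2 = 6 combinations, because each needs an increase as well as a value.

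**2. Pre-existing cases per arm**

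SAP 4.2 gives 490 randomized in six groups: 490 / 6 = 81.7, about 82 per arm. Assumptions, none of them in the documents: a proportion p of subjects is above 450 ms at baseline, 80% of these exceed it again, and 2% of the others are new cases.

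- Pre-existing cases per arm = 0.8 x p x 82.
- Reported rate in the >450 row = 0.8 x p + 0.02 x (1 - p).
- Pre-existing share = 0.8 x p / reported rate.

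| p | Cases per arm | Reported rate | Pre-existing share |
|---|---|---|---|
| 2% | 1.3 | 3.6% | 45% |
| 4% | 2.6 | 5.1% | 63% |
| 6% | 3.9 | 6.7% | 72% |

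**3. Dilution**

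Take p = 4% and suppose that an active arm doubles the new-case rate from 2% to 4%. The reported rates are 0.032 + 0.02 x 0.96 = 5.1% and 0.032 + 0.04 x 0.96 = 7.0%. A ratio of 2 becomes 7.04 / 5.12 = 1.4, while the difference stays near 2 percentage points.

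**4. A second illustration with other assumptions**

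A simulation with no drug effect used mean QTcF 405-425 ms, between-subject SD 18-20, within-subject SD 8-10 and three post-baseline ECGs. The >450 row held 2.2% to 21.9% of subjects under the SAP rule and 1.4% to 11.2% under the laboratory-type rule. Between 34% and 50% of those counted were already above 450 ms at baseline. The category-worsening rule would keep slightly more subjects than the laboratory-type rule, because it retains those who move from above 450 ms to a higher category.

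**The case against.** The strongest defence is that the onset condition still binds. On that reading, the clause about the highest value only says which measurements are eligible, and a stable 455 ms has no onset on treatment. This reading is possible, but the text does not make it the rule. The category definitions and the operational clause use the post-baseline maximum without a baseline test, and SAP 5.6.8.1 shows that the authors wrote such a test when they wanted one. The defence establishes ambiguity, which itself needs resolving.

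Three further objections stand in part:

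- **Scope.** The change rows and the six combinations already use baseline and are sound. The listings and the table of changes let a reader find pre-existing cases, though no planned summary separates them.
- **Bias.** A reader might infer that the table is biased for or against a dose. The documents do not support that. Allocation is randomized with a concurrent placebo arm, so pre-existing prolongation is balanced on average. Chance imbalance remains: at an assumed 4%, an arm has 82 x 0.04 = 3.3 such subjects with SD = sqrt(82 x 0.04 x 0.96) = 1.8. That is noise in small counts, not a systematic shift. Protocol 11.3.5 plans descriptive safety summaries, and SAP 10.1 treats everything beyond the main analysis as exploratory.
- **Size.** A reader might also infer that about half or more of the reported cases would be pre-existing. That share rests wholly on assumed inputs: it is 45-72% under one set and 34-50% under another.

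Copying the laboratory condition row by row would also cause harm. A subject going from 455 to 501 ms would leave the >450 row but stay in >480 and >500, which breaks the cumulative display. Applied to the combinations, it would remove a genuine increase of 46 ms.

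**Conclusion.** The point holds as an internal inconsistency in SAP 5.6.7.1 with a limited consequence. Taken as operationally written, the rule counts prolongation present before treatment as treatment-emergent in the >450, >480 and >500 ms rows, contrary to the SAP's own laboratory convention. Incidence in those rows is inflated and the relative contrast between arms is diluted. It does not touch the change rows, the combinations or the primary analysis.

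The direction follows from the text alone. The size does not: about 1 to 4 pre-existing cases per arm depends on an assumed 2-6% baseline prevalence and 80% persistence. The change is worth making because the table is reported by dose in a dose-selection study and should contain what its label says.

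**What to change.** In SAP 5.6.7.1, for the absolute QTcF categories only, count a subject as treatment-emergent when the worst post-baseline category is higher than the baseline category (450 ms or less, H, HH, HHH). Then report that subject cumulatively in every category reached, as the section intends. Leave the >30 and >60 ms categories and the six combinations unchanged.

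Add a table of baseline category by worst post-baseline category, by treatment group, to SAP 10.9.3 and 13.10. The baseline ECG is already scheduled on Day -1 (Protocol 8.1.4.1), so no new data are needed.

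The same paragraph should be corrected where it cites Sections 11.2 and 11.4 for double-blind start and end. Those sections define run-in start and randomization, and the intended ones are 11.5 and 11.6.

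The cost is one sentence, one program condition and one extra table. Counts in the absolute rows will be slightly lower. A subject whose QTcF rises within the same category will no longer appear in those rows but stays visible in the shift table.
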